6.5. Continuation of Treatment

Study drug dosing will continue in the absence of disease progression or toxicity warranting discontinuation therapy.

6.5.1. Every 8 Weeks for Cohorts 1, 2 and 4 Every 9 Weeks for Cohort 3

For subjects continuing treatment, or subjects who discontinue all treatment prior to disease progression but remain on study, the following will be performed and documented every 8 weeks (± 5 days) for subjects in Cohorts 1 (andecaliximab monotherapy), 2 (combination therapy andecaliximab and SP), and 4 (combination therapy andecaliximab and nivolumab), and every 9 weeks (± 5 days) for subjects in Cohort 3 (combination therapy andecaliximab and SOX):

- Assessment of tumor response
 - CT or MRI
- If not collected in the last 2 weeks, obtain blood samples for:
 - Chemistry (See Section 6.12.8)
 - Hematology (See Section 6.12.8)
 - Coagulation (See Section 6.12.8)
 - Blood biomarkers (See Section 3.11)
 - For Cohort 4 (combination therapy andecaliximab and nivolumab): Thyroid function tests (See Section 6.12.8)
- Review of concomitant medication(s)
- Record any SAEs and all AEs related to protocol mandated procedures

6.6. Assessments for Premature Discontinuation from Study

If a subject discontinues study dosing (for example, as a result of an AE), every attempt should be made to keep the subject in the study and continue to perform the required study-related follow-up and procedures (see Section 3.6). If this is not possible or acceptable to the subject or investigator, the subject may be withdrawn from the study. It is recommended that the investigator consults with the medical monitor prior to removing the subject from study for any reason except subject withdrawal of consent.

6.7. Criteria for Discontinuation of Study Treatment

See Sections 3.5 and 3.7 for discontinuation criteria.

6.8. End of Treatment

EOT assessments will be requested from subjects in all cohorts who discontinue all treatment prior to disease progression. These assessments should be completed as soon as possible after the decision is made. Every attempt should be made to keep the subject in the study and continue to perform tumor evaluation by CT or MRI every 8 weeks (for Cohorts 1, 2, and 4) or every 9 weeks (for Cohort 3) until disease progression.

The following will be performed and documented at the EOT visit:

- Modified PE capturing changes from prior examinations and weight
- Vital signs including blood pressure, respiratory rate, pulse, and temperature
- ECOG Performance Status
- If not conducted in the last 2 weeks, obtain blood samples for:
 - Chemistry (See Section 6.12.8)
 - Hematology (See Section 6.12.8)
 - Coagulation (See Section 6.12.8)
 - Andecaliximab concentration (See Section 6.12.8)
 - Anti-andecaliximab antibodies (See Section 6.12.8)
 - Blood biomarkers (See Section 3.11)
 - For Cohort 4 (combination therapy andecaliximab and nivolumab): Thyroid function tests (See Section 6.12.8)
- Review of concomitant medication(s)
- Record any SAEs and all AEs related to protocol mandated procedures

6.9. End of Study Visit

The following will be performed and documented at the EOS visit:

- Modified PE capturing changes from prior examinations and weight
- Vital signs including blood pressure, respiratory rate, pulse, and temperature
- 12-lead ECG
- ECOG Performance Status
- Obtain blood and/or urine samples for:
 - Chemistry (See Section 6.12.8)
 - Hematology (See Section 6.12.8)
 - Coagulation (See Section 6.12.8)
 - Andecaliximab concentration (See Section 6.12.8)

- Anti-andecaliximab antibodies (See Section 6.12.8)
- Blood biomarkers (See Section 3.11)
- Urine pregnancy test for females of childbearing potential (See Section 6.12.8)
- Urinalysis (See Section 6.12.8)
- For Cohort 4 (combination therapy andecaliximab and nivolumab): Thyroid function tests (See Section 6.12.8)
- CT or MRI (if not conducted within the previous 28 days)
- Tumor tissue biopsy (at progression for Cohorts 2 and 3, CCI)
- Review of concomitant medication(s)
- Record any SAEs and all AEs related to protocol mandated procedures

6.10. Follow-up Visits

6.10.1. 30-Day Safety Follow-Up

A safety follow-up visit will be performed 30 days (\pm 7 days) after the last dose of andecaliximab. The 30-day safety follow-up visit may be substituted by a scheduled study visit if it occurs within the same window. The following will be performed and documented at the 30-day follow-up visit:

- Modified PE capturing changes from prior examinations and weight
- Vital signs including blood pressure, respiratory rate, pulse, and temperature
- ECOG Performance Status
- Obtain blood and/or urine samples for:
 - Chemistry (See Section 6.12.8)
 - Hematology (See Section 6.12.8)
 - Anti-andecaliximab antibodies (See Section 6.12.8)
 - Urine pregnancy test for females of childbearing potential (See Section 6.12.8)
 - Urinalysis (See Section 6.12.8)
 - For Cohort 4 (combination therapy andecaliximab and nivolumab): Thyroid function tests (See Section 6.12.8)
 - For Cohort 4 (combination therapy andecaliximab and nivolumab): Blood biomarkers (See Section 3.11)

- Review of concomitant medication(s)
- Record any SAEs and all AEs

For subjects who come off study for reasons other than disease progression, the site should also obtain information on post-study anti-cancer therapies, surgeries, and date of definitive disease progression (if known).

6.10.2. Cohort 4 (Combination Therapy Andecaliximab and Nivolumab) Only: 5-Month Safety Follow-Up

A safety follow-up visit will be performed 5 months (\pm 7 days) following the last dose of nivolumab for subjects in Cohort 4 (combination therapy andecaliximab and nivolumab). The 5-month follow-up visit may be substituted by a scheduled study visit if it occurs within the same window. The following will be performed and documented at the 5-month follow-up visit:

- Obtain blood and/or urine samples for:
 - Chemistry (See Section 6.12.8)
 - Hematology (See Section 6.12.8)
 - Anti-andecaliximab antibodies (See Section 6.12.8)
 - Urine pregnancy test for females of childbearing potential (See Section 6.12.8)
 - Urinalysis (See Section 6.12.8)
 - Thyroid function tests (See Section 6.12.8)
 - Blood biomarkers (See Section 3.11)
- Review of concomitant medication(s)
- Record any SAEs and all AEs

6.10.3. Long Term Follow-Up

Long term follow-up (LTFU) for OS begins after the EOS visit, or the last visit on study if EOS does not occur. Subjects will be contacted via phone call every 3 months for determination of long term survival status and record of any other anti-cancer therapy, cancer-related surgery for up to 5 years after the EOS visit.

Subjects who are not deceased by the time Gilead has made the determination the study will be ended will receive a final follow-up phone call to assess survival status and communicate the sponsor's decision.

The investigator will make every effort to contact the subject or a close relative or caretaker by phone to collect survival information. The investigator should show due diligence by documenting in the source documents steps taken to contact the subject (ie, dates of phone calls, registered letters, etc).

6.11. Replacement of Subjects

In Cohort 1 (andecaliximab monotherapy), if a subject is withdrawn from the study for any reason other than a DLT prior to completion of the DLT assessment window, a replacement subject will be enrolled.

6.12. Description of Study Procedures

6.12.1. Informed Consent

All subjects must sign and date the most recent IRB/IEC-approved informed consent form before any study specific procedures are performed. CCI

6.12.2. Re-Screening Criteria

Subjects who fail to meet eligibility or complete the initial screening will be permitted to rescreen provided that the reason for screen failure has been resolved and no new exclusions have been identified. If the subject is rescreened > 28 days from their original screening date (date of informed consent), all screening activities, including informed consent, need to be repeated.

Subject eligibility must be determined by results received from the central lab. However, if there have been 2 failed attempts to obtain test results from the central lab, eligibility may be determined using local lab results, with documentation of failed attempts, local lab results and sponsor approval.

6.12.3. Medical & Medication History

A complete medical and surgical history will be obtained by the investigator or designee at screening, including disease history, and recorded on the electronic case report form (eCRF).

All medications taken within 28 days prior to screening and during the screening period will be obtained prior to Day 1 and recorded on the eCRF. For all cohorts, at each study visit the site will capture any and all medications taken by the subject since the last visit or during the visit (as applicable). Concomitant medications include prescription and non-prescription medications, vitamins and minerals.

In addition, supportive therapies given during the course of the study (eg, blood transfusion, growth factor) should be collected and recorded on the eCRF.

6.12.4. Physical Examination

A complete PE will be performed for all cohorts at screening. This will include assessment of clinical signs and symptoms. The exam will be performed by a physician or designee qualified to perform assessments. Breast, genital, and rectal examinations are not required, unless warranted in opinion of the healthcare provider.

For Cohorts 1, 2, and 4, a modified physical exam capturing changes from prior exams will be performed on Day 1 and 15 of each 28-day cycle, at the EOT visit, at the EOS visit, and at the 30-day safety follow-up visit.

For Cohort 3, a modified physical exam capturing changes from prior exams will be performed on Day 1 of each 21-day cycle, at the EOT visit, at the EOS visit, and at the 30-day safety follow-up visit.

Weight (without shoes) should be measured with each PE (complete and modified) and reported in kilograms. Height (without shoes) should be measured at screening only and reported in centimeters. Weight will be collected any time a complete or modified PE is performed.

Pre dose abnormal findings will be reported on the medical history page of the eCRF. Any changes from pre dose baseline PE which represent a clinically significant deterioration will be documented on the AE page of the eCRF.

6.12.5. Vital Signs

Vital signs, including blood pressure, pulse, respiratory rate, and temperature, will be measured by the investigator or qualified designee as per standard institutional guidelines at each study visit as indicated in [Appendix 2-Appendix 5](#).

All measurements will be recorded on the appropriate eCRF page with appropriate source documentation. Any abnormal measurements may be repeated and reported as AEs if appropriate. All measures of blood pressure will be performed using standard sphygmomanometry. Measurements of blood pressure should be taken per institutional guidelines.

6.12.6. Electrocardiogram Assessment

For all cohorts, a single 12-lead ECG will be collected at screening, on Day 1 of each cycle, and at the EOS Visit, per standard practice.

The investigator or qualified designee will review all ECGs and retain the tracing with the source documents. Appropriate data will be reported on the eCRF.

6.12.7. Performance Status

Performance status will be scored using the ECOG performance status scale index at each study visit (for all cohorts) as indicated in [Appendix 2-Appendix 5](#). ECOG used to determine eligibility must be the performance status during the screening period.

6.12.8. Laboratory Assessments

The central laboratory will be responsible for chemistry, hematology, coagulation, urinalysis, and serum pregnancy testing (per [Table 6-1](#)) as well as processing and/or storage of other study samples. Specific instructions for processing, labeling, and shipping samples will be provided in a central laboratory manual.

If central laboratory results are not available, local laboratories may be used for dosing decisions. Local laboratory assessments resulting in a dose change or as part of an adverse event assessment, which is not supported by central lab results, will be reported on the eCRF.

Urine pregnancy test will be performed at the site.

The date and time of blood and/or urine sample collection will be recorded in the subject's source documentation and reported to the central laboratory. Screening laboratory samples should be obtained within 28 days prior to enrollment. Specified Day 1 pre dose samples may be drawn up to 2 days prior to the Day 1 visit (see [Appendix 2-Appendix 5](#)). The tests will be analyzed using standard procedures. White blood cell differentials will be reported as absolute counts.

Blood samples will be obtained for chemistry, hematology, coagulation, pregnancy testing for female subjects, andecaliximab concentration and anti-andecaliximab antibodies, and serum and plasma biomarkers as indicated in [Appendix 2-Appendix 5](#). Urine samples will be obtained for urinalysis and pregnancy testing for female subjects as indicated in [Appendix 2-Appendix 5](#).

Table 6-1. Analytes

Serum Chemistry	Urinalysis	Hematology	Other
Albumin	Color and appearance	WBC	Serum β -hCG ^c (females)
Alkaline phosphatase	Specific gravity	Hemoglobin	Urine pregnancy test ^c (females)
ALT	pH	Hematocrit	Andecaliximab concentration
AST	Occult blood	Platelet	Anti-andecaliximab antibodies
Bicarbonate	Protein	ANC	Serum and plasma biomarkers
BUN	Glucose		
Calcium	Bilirubin	Differential	COHORT 4 ONLY: Thyroid Function Tests: (TSH, T3, free T4) ^d
Chloride	Leukocyte esterase	Eosinophils	
Creatinine ^a	Nitrite	Lymphocytes	
Glucose	Urobilinogen	Monocytes	
Amylase	Ketones	Neutrophils	
Lipase	Microscopic ^b		
Magnesium		Coagulation	
Phosphorus		PT/INR	
Potassium		aPTT	
Sodium			
Total bilirubin			
Direct bilirubin			
Total protein			
CA19-9			
CEA			
hsCRP			
COHORTS 3 & 4 ONLY:			
AFP			

Abbreviations: AFP = alpha-fetoprotein; ANC = absolute neutrophil count; ALT = alanine aminotransferase; aPTT = Activated Partial Thromboplastin Time; AST = aspartate aminotransferase; BUN = blood urea nitrogen; CA19-9 = carbohydrate antigen 19-9; CEA = carcinoembryonic antigen; β -hCG = betahuman chorionic gonadotropin; HER2 = human epidermal growth factor receptor 2; INR = International Normalized Ratio; hsCRP = High sensitivity C-Reactive protein; PT = Prothrombin Time; TSH = thyroid-stimulating hormone; WBC = white blood cell

a Estimated creatinine clearance (CLcr)/glomerular filtration rate will be calculated based on the Cockcroft-Gault formula using actual body weight: $CLcr (mL/min) = (140 - \text{age [years]}) * \text{weight (kg)} / (\text{serum creatinine [mg/dL]} * 72)$. If the subject is female, multiply the quantity by 0.85.

b Reflex testing based on other abnormalities

c Females of child-bearing potential only. Serum pregnancy will be conducted at Screening. Urine pregnancy tests will be performed at the time points specified in Section 6.12.8.1 and Appendix 2-Appendix 5.

d TSH, T3, free T4 will be test by the central laboratory at screening. At the every 8 week visit and beyond, T3 and T4 will be tested reflexively based on abnormal TSH results.

At any time during the study, abnormal laboratory parameters that are clinically relevant (eg, lead to clinical symptoms or signs, require therapeutic intervention), and constitute an AE must be recorded in the eCRF. All laboratory tests must be reviewed for clinical significance by the investigator or qualified designee.

6.12.8.1. Pregnancy Test

All females of childbearing potential (see [Appendix 9](#)) will have a serum pregnancy test at screening.

For female subjects in Cohort 1 (andecaliximab monotherapy), urine pregnancy tests will be performed on Cycle 1 Day 1 Pre Dose, at the EOS visit and at the 30-day safety follow-up visit.

For female subjects in Cohort 2 (combination therapy andecaliximab and SP), urine pregnancy tests will be performed Pre Dose on Days 1 and 15 of each 28-day cycle, at the EOS visit, and at the 30-day safety follow-up visit.

For female subjects in Cohort 3 (combination therapy andecaliximab and SOX), urine pregnancy tests will be performed Pre Dose on Day 1 of each 21-day cycle, at the EOS visit, and at the 30-day safety follow-up visit.

For female subjects in Cohort 4 (combination therapy andecaliximab and nivolumab), urine pregnancy tests will be performed Pre Dose on Days 1 and 15 of each 28-day cycle, at the EOS visit, and at the 30-day and 5-month safety follow-up visits.

The results must be confirmed as negative prior to administration of study drug on the respective days the test is performed.

6.12.8.2. HER2 Testing

Prior to enrollment in Cohorts 1 (andecaliximab monotherapy), 2 (combination therapy andecaliximab and SP), and 3 (combination therapy andecaliximab and SOX), the subject's tumor should have been tested for HER2 status with approved IHC and in situ hybridization (ISH) kits. HER2 positivity is defined as IHC3+ or IHC2+/ISH+ (ISH positivity is defined as HER2:CEP17 ratio of ≥ 2.0). Results for HER2 status obtained prior to signing informed consent are acceptable if obtained with approved IHC and ISH kits. HER2 status may be determined during screening by testing the tumor at the central lab or a local lab with approved IHC and ISH kits.

6.12.8.3. Andecaliximab Pharmacokinetics

For Cohort 1 (andecaliximab monotherapy), plasma samples for andecaliximab PK will be collected prior to andecaliximab dosing and 30 (± 15) minutes after the end of infusion on Day 1 of Cycles 2, 3, 5, 7, and every 3 cycles thereafter and anytime at the EOT visit (if not conducted in the last 2 weeks), and EOS visit. Additionally, PK plasma samples will be collected at the following time points in Cycle 1 only: 30 (± 15) minutes after the end of infusion on Day 1; anytime on Days 2, 4, and 8; prior to dosing and 30 (± 15) minutes after the end of infusion on Day 15.

For Cohort 2 (combination therapy andecaliximab and SP), plasma samples for andecaliximab PK in Cycle 1 will be collected 30 (± 15) minutes after the end of andecaliximab infusion on Day 1 and prior to andecaliximab dosing on Day 15. Additionally, plasma samples for

andecaliximab PK will be collected prior to andecaliximab dosing and 30 (± 15) minutes after the end of infusion on Day 1 of Cycles 2, 3, 5, 7, and every 3 cycles thereafter, and anytime at the EOT visit (if not conducted in the last 2 weeks), and EOS visit.

For Cohort 3 (combination therapy andecaliximab and SOX), plasma samples for andecaliximab PK in Cycle 1 will be collected 30 (± 15) minutes after the end of andecaliximab infusion on Day 1. Additionally, plasma samples for andecaliximab PK will be collected prior to andecaliximab dosing and 30 (± 15) minutes after the end of infusion on Day 1 of Cycles 2, 3, 5, 7, and every 3 cycles thereafter, and anytime at the EOT visit (if not conducted in the last 2 weeks), and EOS visit.

For Cohort 4 (combination therapy andecaliximab and nivolumab), plasma samples for andecaliximab PK in Cycle 1 will be collected 30 (± 15) minutes after the end of andecaliximab infusion on Day 1, anytime on Day 8, and prior to andecaliximab dosing and 30 (± 15) minutes after the end of infusion on Day 15. Additionally, plasma samples for andecaliximab PK will be collected prior to andecaliximab dosing and 30 (± 15) minutes after the end of infusion on Day 1 and Day 15 of Cycles 2, 3, 5, 7, and every 3 cycles thereafter, and anytime at the EOT visit (if not conducted in the last 2 weeks), and EOS visit.

6.12.8.4. Anti-Andecaliximab Antibodies

For all cohorts, blood samples for anti-andecaliximab antibodies will be collected prior to dosing on Day 1 of Cycles 1, 2, 3, 5, 7, and every 3 cycles thereafter, at the EOT visit (if not conducted in the last 2 weeks), at the EOS visit, and at the 30 day safety follow-up visit.

For Cohort 4 (combination therapy andecaliximab and nivolumab), blood samples for anti-andecaliximab antibodies will also be collected at the 5-month safety follow-up visit.

6.12.8.5. Tumor Tissue Biopsy

Cohorts 1 (andecaliximab monotherapy) and 4 (combination therapy andecaliximab and nivolumab): Tumor tissue biopsy will be collected within 28 days prior to the first dose of andecaliximab (Pre Dose, Cycle 1 Day 1) in both Cohorts 1 and 4, on Cycle 2 Day 15 (+ 5 days) for Cohort 1, and at 6 weeks (± 1 week) after the first dose of andecaliximab for Cohort 4. A normal gastric tissue biopsy will also be collected within 28 days prior to the first dose of andecaliximab (Pre Dose, Cycle 1 Day 1) in both Cohorts 1 and 4. **CCI**

Cohorts 2 (combination therapy andecaliximab and SP) and 3 (combination therapy andecaliximab and SOX): Tumor tissue biopsy will be collected within 28 days prior to the first dose of andecaliximab (Pre Dose, Cycle 1 Day 1) and at EOS with documented disease progression. A normal gastric tissue biopsy will also be collected within 28 days prior to the first dose of andecaliximab (Pre Dose, Cycle 1 Day 1). Endoscopic samples (minimum 4, but 6-8

encouraged) or 18 gauge needle biopsies (4 passes) of metastases to liver or lymph nodes are acceptable and are to be processed as described in the laboratory manual.

6.12.8.6. Archival Tumor Tissue

Archival tumor tissue formalin-fixed paraffin embedded (FFPE) blocks will be collected from all subjects and shipped to the central laboratory for sectioning. If blocks are not available to be shipped, 15 x 5-micron slides and 5 x 10-micron slides prepared within 2 weeks from the archival tissue block are requested. Efforts to acquire the archival tissue should begin on Day 1 of Cycle 1.

6.12.8.7. Biomarkers

Samples for biomarker analysis will be obtained as indicated in Section 3.11.

6.12.9. Tumor Response Assessment

6.12.9.1. Tumor Imaging

Either contrast-enhanced CT or gadolinium-enhanced MRI of the chest, abdomen, and pelvis will be performed at screening (scans taken as part of medical practice within 28 days of Day 1 are acceptable), every 8 weeks (for Cohorts 1, 2, and 4) or every 9 weeks (for Cohort 3), and at the EOS visit if one has not been performed within the previous 28 days. Tumor burden will be evaluated solely based on radiographic imaging per RECIST v1.1. Chest x-ray, ultrasound, endoscopy, laparoscopy, positron-emission tomography, radionuclide scans, or tumor markers will not be considered for response assessment.

For radiographic evaluations, the same method of assessment and the same technique (eg, scan type, scanner, subject position, dose of contrast, injection/scan interval) should be used to characterize each identified and reported lesion at baseline and during study treatment and follow-up.

Scans taken as part of standard medical practice up to 28 days prior to enrollment can be used for screening as long as they meet all study requirements. During the treatment phase, scans may be performed at time points other than every 8 or 9 weeks as clinically indicated to assess tumor progression.

If a subject has discontinued all study treatments prior to definitive disease progression, the subject shall remain on study until at least 1 of the criteria for discontinuation from study is met (Section 3.7). Every attempt should be made to keep the subject in the study and continue to perform tumor evaluation by CT or MRI every 8 weeks (for Cohorts 1, 2, and 4) or every 9 weeks (for Cohort 3) until disease progression. If this is not possible or acceptable to the subject or investigator, the subject may be withdrawn from the study. It is recommended that the investigator consults with the medical monitor prior to removing the subject from study for any reason except subject withdrawal of consent.

6.12.9.2. Efficacy Measurements for Cohort 4 (Combination Therapy Andecaliximab and Nivolumab) ONLY

RECIST version 1.1 {Eisenhauer 2009} (Appendix 10) will be used for assessment of tumor responses for the purposes of study evaluation, managing patients on protocol treatment, and decision making for discontinuation of study therapy due to disease progression, with some modifications to account for atypical responses which may occur with immune-based therapies {Swaika 2015}. Given that anti PD-1 agents produce antitumor effects by potentiating endogenous cancer-specific immune responses, the response patterns seen with these agents may extend beyond the typical time course of responses seen with cytotoxic agents. In addition, anti-PD-1 therapies can occasionally manifest a clinical response after an initial increase in tumor burden or even the appearance of new lesions (“tumor flare” or “pseudoprogression”) {Topalian 2014}. In these cases, standard RECIST may not provide an accurate response assessment of anti PD-1 agents.

Therefore, for subjects enrolled in Cohort 4, RECIST 1.1 will be used (Appendix 10) with the following adaptations:

If imaging shows a CR or PR, tumor imaging should be repeated at least 4 weeks (≥ 4 weeks) later to confirm response, per RECIST 1.1 guidelines. Subjects will then return to regular scheduled imaging every 8 weeks starting with the next protocol-specified imaging time-point (every 8 weeks from Day 1).

Subjects who obtain a confirmatory scan do not need to undergo scheduled imaging assessment ≤ 2 weeks later (eg, if a subject obtains a scan at Week 22 to confirm a Week 16 response, they will not also be required to complete the scheduled Week 24 scan).

If imaging shows progressive disease (PD), it is at the discretion of the investigator to keep the subject on study treatment or to stop study treatment until imaging is repeated ≥ 4 weeks later in order to confirm PD (adapted from the immune-related response criteria recommendations) {Wolchok 2009}. Patients that are deemed clinically unstable or who have biopsy-proven new metastatic lesions are not required to have repeat imaging for confirmation. The decision to continue a subject on study while awaiting PD confirmation will be based on clinical judgment of a subject’s overall clinical condition, including performance status, clinical symptoms, and laboratory data.

At a minimum, subjects must meet the following criteria for continued treatment on study after disease progression is identified at a tumor assessment:

- Absence of signs and symptoms (including worsening laboratory values) indicating disease progression
- No decline in ECOG performance status
- Absence of rapid progression of disease or of progressive disease at critical anatomical sites (eg, cord compression) requiring urgent alternative medical intervention

Study treatment may continue under the following circumstances after repeat/confirmatory imaging (≥ 4 weeks after initial scan showing PD):

- If repeat imaging shows $< 20\%$ tumor burden increase compared to nadir, stable or improved previous new lesion (if identified as cause for initial PD), and stable/improved non-target disease (if identified as cause for initial PD), treatment may be continued and/or resumed (PD is not confirmed).
- If repeat imaging confirms PD due to any of the scenarios listed below, subjects will be discontinued from study therapy with the following exception: if the subject is achieving a clinically meaningful benefit, and there is no further increase in the tumor burden at the confirmatory tumor imaging compared to the initial PD assessment, an exception to continue treatment may be considered following consultation with the Sponsor. In this case, if treatment is continued, tumor imaging should continue to be performed at the protocol specified intervals.

In determining whether or not the tumor burden has increased or decreased, site study team should consider all target lesions as well as non-target lesions.

If repeat imaging shows an objective response or stable disease relative to nadir, treatment with study medication may continue and subjects will return to regular scheduled imaging every 8 weeks starting with the next protocol-specified imaging time-point. Subjects who obtain a confirmatory scan do not need to undergo scheduled imaging assessment ≤ 2 weeks later (eg, if a subject obtains a scan at Week 14 to confirm a Week 8 PD and progression is not confirmed, they will not also be required to complete the scheduled Week 16 scan).

Progressive Disease is confirmed at repeat imaging if:

- Tumor burden remains $\geq 20\%$ (and at least 5 mm absolute increase) compared to nadir
- Non-target disease resulting in initial PD is worse (qualitative)
- New lesion(s) resulting in initial PD is worse (qualitative)
- Additional new lesion(s) since last evaluation

If repeat imaging confirms PD, subjects will be discontinued from study therapy.

Table 6-2. Imaging and Treatment after First Radiologic Evidence of Progressive Disease

	Clinically Stable		Clinically Unstable	
	Imaging	Treatment	Imaging	Treatment
First radiologic evidence of PD by RECIST 1.1	Repeat imaging at ≥ 4 weeks at site to confirm PD	May continue study treatment at the local site Investigator's discretion while awaiting confirmatory tumor imaging by site by irRECIST.	Repeat imaging at ≥ 4 weeks to confirm PD per physician discretion only	Discontinue treatment
Repeat tumor imaging confirms PD by RECIST (see modifications in protocol)	No additional imaging required	Discontinue treatment (exception is possible upon consultation with sponsor)	No additional imaging required	N/A
Repeat tumor imaging shows SD, PR, or CR by RECIST (see protocol for details)	Continue regularly scheduled imaging assessments	Continue study treatment at the local site Investigator's discretion	Continue regularly scheduled imaging assessments	May restart study treatment if condition has improved and/or clinically stable per Investigator's discretion. Next tumor image should occur according to the every 8 week imaging schedule

In subjects who discontinue study therapy early without documented disease progression, every effort should be made to continue monitoring their disease status by radiologic imaging following guidelines for end of study follow-up (Section 6.6).

When feasible, subjects should not be discontinued until progression is confirmed; investigators should discuss with the Gilead Medical Monitor prior to subject discontinuation.

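### Cohort 4: the rule for unconfirmed progression does not exclude a further new lesion, so it overlaps with the protocol's own list for confirmed progression

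*Protocol*

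**What the plan says.** Protocol Section 6.12.9.2 allows a Cohort 4 subject with a first radiologic PD to stay on treatment, at the investigator's discretion, until a repeat scan at least 4 weeks later. It then gives two bullets.

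- **First bullet (PD not confirmed).** It has three conditions: burden less than 20% above nadir; a previous new lesion stable or improved, if that lesion caused the initial PD; and the same for non-target disease. It closes: "stable/improved non-target disease (if identified as cause for initial PD), treatment may be continued and/or resumed (PD is not confirmed". Additional new lesions are not mentioned, and no sponsor contact is required.
- **Second bullet (PD confirmed).** "If repeat imaging confirms PD due to any of the scenarios listed below, subjects will be discontinued from study therapy". The only way round this is an exception for a subject with clinically meaningful benefit, provided that "there is no further increase in the tumor burden at the confirmatory tumor imaging compared to the initial PD assessment"; in that case "an exception to continue treatment may be considered following consultation with the Sponsor".

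On judging whether burden has changed, the section says the "site study team should consider all target lesions as well as non-target lesions".

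The list of findings that confirm PD has four items: burden still at least 20% (and at least 5 mm) above nadir; worse non-target disease, where that caused the initial PD; a worse new lesion, where that caused it; and "Additional new lesion(s) since last evaluation". The section then repeats that confirmed PD ends study therapy. In Table 6-2, treatment continues after the repeat scan only for stable disease, partial response or complete response. In Appendix 10, any new lesion gives an overall response of PD.

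**The concern.** The first bullet is a permission in its own right and carries its own label. A site that checks its three conditions and finds them met has followed a stated rule, although the same scan may show a lesion that the list counts as confirmed PD. By that route the site skips all three conditions of the exception: clinical benefit, no further rise in burden, and sponsor consultation.

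The misreading is plausible in this cohort. The section itself explains that responses to anti-PD-1 agents can follow the appearance of new lesions, and it asks sites, where feasible, not to discontinue subjects before progression is confirmed. What is at stake is dosing beyond progression in individual patients, together with the exposure and disposition data that follow from it. The choice to treat new lesions on the repeat scan as confirmed PD is not in dispute.

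**Working it through.** The plan gives no figure to reproduce here. The check is whether one scan can satisfy both rules, and what follows if it does.

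**Step 1. The rules side by side (Section 6.12.9.2).**

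| Feature of the repeat scan | First bullet (not confirmed) | List (confirmed if any one holds) |
|---|---|---|
| Burden against nadir | less than 20% | at least 20% and at least 5 mm |
| Non-target disease that caused initial PD | stable or improved | worse |
| New lesion that caused initial PD | stable or improved | worse |
| Additional new lesion | no condition | present |

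The last row has no counterpart in the first bullet.

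**Step 2. All combinations.** Take 3 burden states (under 20%; at least 20% but under 5 mm; at least 20% and at least 5 mm), 3 non-target states (not the cause; cause and stable or improved; cause and worse), the same 3 states for the previous new lesion, and an additional new lesion yes or no: 3 × 3 × 3 × 2 = 54.

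- States meeting the first bullet: 1 × 2 × 2 × 2 = 8.
- Of these, states also meeting the list: the 4 with an additional new lesion.
- With a no-additional-new-lesion condition in the bullet: 0 of 54 meet both.

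The missing condition is therefore the only source of overlap. These are counts of logical combinations, not frequencies in patients.

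**Step 3. Does the burden condition catch the new lesion?** The sentence on burden names target and non-target lesions only. Even if new lesions were added to the burden, any case with a total under 20% above nadir would still pass. With a nadir of 50 mm, that is any total under 60 mm.

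**Step 4. A scan on which the decisions differ (assumed sizes, non-target disease unchanged).** Nadir 50 mm; initial PD scan 52 mm with one new lesion; repeat scan 58 mm, first new lesion stable, second new lesion present.

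- First bullet: (58 − 50)/50 = 16%, under 20%, and the initial cause is stable. PD is not confirmed and treatment may continue.
- List: an additional new lesion is present. PD is confirmed.
- Exception: 58 − 52 = 6 mm, or 6/52 = 11.5%, above the initial PD scan. The exception is closed and treatment must stop.

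If the repeat were 52 mm or less and there was clinical benefit, the exception would be open. The two routes might then differ by one sponsor consultation and no infusions.

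**Step 5. Upper bound on infusions.** Inputs: both drugs every 2 weeks, so doses fall on even weeks; scheduled scans at Weeks 8, 16 and 24; a scheduled scan no more than 2 weeks after the repeat may be skipped. The protocol's own example of the last point is a waived Week 16 scan "if a subject obtains a scan at Week 14 to confirm a Week 8 PD and progression is not confirmed". Assume first PD at Week 8 and dosing on schedule.

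| Repeat scan | Next scheduled scan | Doses from the repeat until then | Number |
|---|---|---|---|
| Week 12 | Week 16 | 12, 14 | 2 |
| Week 13 | Week 16 (3 weeks later, not waived) | 14 | 1 |
| Week 14 | Week 24 (Week 16 waived) | 14, 16, 18, 20, 22 | 5 |
| Week 15 | Week 24 (Week 16 waived) | 16, 18, 20, 22 | 4 |

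The lower bound is 0 in every row.

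**The case against.** The strongest reply is that the section resolves itself. The first bullet is permissive, the second is mandatory and triggered by any one listed finding, and a scan on the confirmed list cannot sensibly be called unconfirmed. Section 6.12.9.2 also keeps RECIST 1.1 as the base rule with adaptations, and the bullet forgives only a previous new lesion. This settles what was intended and is why the point is minor. It does not remove the conflict. The discontinuation rules apply once PD is confirmed, and a site that stops at the first bullet has been told that it is not. Appendix 10 cannot decide the matter alone, because the bullet already departs from its any-new-lesion rule.

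The sentence on burden does not expressly exclude new lesions, and the plan cites immune-related criteria whose definition of burden it does not reproduce. That caveat is fair, but counting new lesions would narrow the gap without closing it (Step 3).

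Table 6-2 mentions the exception with sponsor consultation and no burden condition. That row refers the reader back to the protocol's modifications, so the condition in the text still governs.

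The scan in Step 4 is constructed, and opposite decisions need several things to coincide. That stands. So do two safeguards. The clinical criteria introduced by "At a minimum, subjects must meet the following criteria for continued treatment on study after disease progression is identified" apply under either label, and Section 6.12.9.1 allows earlier scans when clinically indicated.

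**Conclusion.** The concern holds, as a minor point. As written, a repeat scan with burden under 20% above nadir, a stable or improved initial cause and an additional new lesion is both unconfirmed and confirmed PD. Where burden has also risen since the initial PD scan, one rule permits dosing and the other forbids it.

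Cohort 4 has at most 10 subjects. The documents do not say how many might show this pattern, and it may be none. Per affected subject the effect runs from 0 to 5 infusions of each drug. The upper end assumes first PD at Week 8, a Week 14 repeat, on-schedule dosing and use of the scan waiver. The consequences are confined to treatment continuation, exposure and disposition. SAP Section 6.2 derives no efficacy endpoint, and SAP Section 3.1.3 limits dose-limiting toxicity evaluation to Cohort 1.

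**What to change.** Add to the first bullet the condition *and no additional new lesion since the last evaluation*. This states the reading that the list, Table 6-2 and Appendix 10 already support, and it leaves the sponsor-consulted exception unchanged. It can go into a clarification letter or the next amendment, and needs no extra scans, visits or data.

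An alternative is to define unconfirmed PD as a repeat scan with none of the four listed findings. That removes the same overlap. It would also classify a separate set of cases that currently meet neither rule: burden at least 20% but less than 5 mm above nadir, with no other finding (4 of the 54 combinations).
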